11.2 Calculation or derivation of pharmacokinetic variables

The PK analyses of the plasma concentration data for selumetinib and N-desmethvl selumetinib will be performed at

Pharmacokinetic analyses will be conducted according to Standard Operating Procedures unless otherwise specified.

Actual sampling times will be used in the plasma PK parameter calculations.

Pharmacokinetic parameters will be determined using standard noncompartmental methods.

Pharmacokinetic parameter units will be consistent with the plasma fied in the bioanalytical data. No conversion of units will be made.

The following PK parameters will be determined for both plasma selumetinib and N-desmethyl selumetinib from fed and fasted plasma concentration data as appropriate:

Area under the plasma concentration-time curve from time zero to AUC infinity, calculated by linear up/log down trapezoidal summation. Area under the plasma concentration-time curve from time zero to $AUC_{(0-t)}$ the time of the last quantifiable concentration, calculated by linear up/log down trapezoidal summation. $AUC_{(0-12)}$ Area under the plasma concentration-time curve from time zero to 12 hours postdose, calculated by linear up/log down trapezoidal summation. Maximum concentration in plasma, obtained directly from the C_{max} observed concentration versus time data. Time to C_{max} . t_{max} CL/F Apparent systemic plasma clearance (selumetinib only). Apparent volume at distribution equilibrium, mean residence time V_{ss}/F (MRT)*CL/F (selumetinib only).

Apparent volume at distribution (selumetinib only).

Date

Terminal half-life. $t_{\frac{1}{2}}$

 λ_z Terminal rate constant.

MRT Mean residence time.

AUC metabolite to parent ratio, N-desmethyl selumetinib MR_{AUC}

AUC/selumetinib AUC.

 MR_{Cmax} C_{max} metabolite to parent ratio, N-desmethyl selumetinib

 C_{max} /selumetinib C_{max} .

No dose adjustment is required for PK parameters which require selumetinib dose for calculation since the selumetinib dose being administered is based on the free base equivalent.

The following PK parameters for plasma selumetinib and N-desmethyl selumetinib will be calculated for diagnostic purposes and listed, but will not be summarized:

t_{1/2}, Interval The time interval of the log-linear regression to determine λ_z .

N Number of data points included in the log-linear regression analysis

used to determine λ_z (a minimum of 3 data points will be used for λ_z

determination).

Coefficient of determination for calculation of λ_z (λ_z and related Rsq

parameters will be reported only if Rsq is 0.800 or more).

%AUC_{ex} Percentage of AUC obtained by extrapolation (if the extrapolated

area is greater than 20% then AUC and related parameters for that

specific profile will not be reported).

Pharmacokinetic parameters will be computed and reported if the anomalous predose concentration value is not greater than 5% of the C_{max} in the profile. If the anomalous predose concentration value is greater than 5% of C_{max} in the profile, PK parameters for the profile will not be reported. If an anomalous concentration value is observed at the terminal phase and is judged as physiologically unreasonable, it will be excluded from computing parameter estimates.

Additional PK parameters may be calculated if deemed appropriate.

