A single dose of selumetinib will be administered on Day 1 of Visits 2 and 3 with a washout period of at least 7 days between administrations.

Outcome variable(s):

Pharmacokinetics

The primary endpoints will be maximum concentration in plasma (C_{max}), area under plasma concentration-time curve from time zero to infinity (AUC), area under plasma concentration-time curve from time zero to the last quantifiable concentration (AUC_(0-t)) determined from selumetinib fed and fasted plasma concentration data

The secondary endpoints will be time to C_{max} (t_{max}), area under the plasma concentration-time curve from time zero to 12 hours postdose (AUC₍₀₋₁₂₎), terminal rate constant (λ_z), terminal half-life (t_{v_z}), apparent systemic plasma clearance (CL/F), apparent volume at distribution equilibrium (V_{ss} /F), apparent volume at distribution (V_z /F), mean residence time (MRT) for selumetinib and AUC, C_{max} , t_{max} , t_{v_z} , AUC₍₀₋₁₂₎, and AUC_(0-t) for the N-desmethyl metabolite.

Safety

The primary safety endpoints will include adverse events, physical examinations, ophthalmologic assessments, vital signs, clinical laboratory assessments, and 12-lead electrocardiograms.

Statistical methods

Following log-transformation, C_{max} , AUC, and AUC_(0-t) of selumetinib and N-desmethyl selumetinib will be separately analysed using a linear mixed-effects analysis of variance model. Transformed back from the logarithmic scale, geometric least-squares means together with confidence intervals (2-sided 95%) for C_{max} , AUC, and AUC_(0-t) will be estimated and presented. Also, ratios of geometric least squares means (fed/fasted) together with confidence intervals (2-sided 90%) will be estimated and presented.

An analysis of selumetinib and N-desmethyl selumetinib t_{max} using the Wilcoxon Signed Rank Test, and the Lehman median estimator of difference (fed-fasted) and 90% confidence intervals will also be presented.

Analyses will be conducted separately for selumetinib and the metabolite N-desmethyl selumetinib, however, it should be noted that sample size was determined according to the precision of the food effect of selumetinib, rather than the metabolite.

These analyses of food effect will require healthy volunteers to have evaluable pharmacokinetic data in both study periods.

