1.2 Rationale for conducting this study

A food effect has previously been observed in patients administered selumetinib (Study D1532C00020) with maximum concentration in the sampled matrix (C_{max}) and area under the concentration-time curve in the sampled matrix from zero to infinity (AUC) being reduced by 62% and 19% respectively under fed conditions. A delay in time to C_{max} (t_{max}) was also observed. The previous food effect study was performed on a formulation that will not be the final to be marketed formulation. The current study will assess the food effect on the to be marketed capsules.

The primary objective of this study to assess any differences in pharmacokinetics (PK) of selumetinib at a dose of 75 mg when administered in the fasted state compared to the fed state.

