3.1 Overall study design and flow chart

This study is designed as a Phase I, open-label, randomized, single-center, 2-period crossover study in healthy male volunteers in order to investigate the effect of food on the PK of a single dose of selumetinib 75 mg. A total of 34 healthy male volunteers aged between 18 and 45 years (inclusive) will be enrolled in the study. Screening procedures will only be performed for healthy volunteers who provide informed consent.

The study will consist of 4 visits. Visit 1 will be a screening visit and will take place within 28 days of Visit 2. Visits 2 and 3 will be the treatment visits and the healthy volunteers will be resident at the study center from Day -1 until Day 3 for both visits. Healthy volunteers will be randomized to 1 of 2 'treatment' sequences on Day 1 of Visit 2 and will receive selumetinib on Day 1 of Visit 2 and Visit 3:

- Sequence 1: 75 mg selumetinib oral dose in a fasted state (Treatment A) followed by a second 75 mg selumetinib oral dose in the fed state (Treatment B) with a washout period of at least 7 days between doses.
- Sequence 2: 75 mg selumetinib oral dose in the fed state (Treatment B) followed by a second 75 mg selumetinib oral dose in the fasted state (Treatment A) with a washout period of at least 7 days between doses.

Visit 4 will be the follow-up visit and will take place 7 to 10 days after discharge from Visit 3.

For Treatment A, selumetinib in the fasted state, healthy volunteers will receive a single oral dose of 75 mg selumetinib after fasting overnight for at least 10 hours and will remain fasted until 4 hours postdose. No water will be allowed from 1 hour before administration until 1 hour after administration, except for water required to swallow the selumetinib capsules.

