12.2.4 Pharmacokinetics

For qualitative variables, the population size (sample size and available data) and the percentage (of available data) for each class of the variable will be presented. Quantitative variables will be summarized using descriptive statistics, including available data, arithmetic mean, SD, coefficient of variation (CV), median, minimum, and maximum values. Additionally, geometric means and geometric CV will be reported for PK variables, except for t_{max} . The geometric mean is calculated as the exponential of the arithmetic mean calculated from data on a log scale. The geometric CV is calculated as $100*[exp(s^2)-1]^{1/2}$; where s is the SD of the data on a log scale. Mean, SD, CV, geometric mean, and geometric CV will not be calculated for t_{max} ; t_{max} will be summarized using median and range.

Plasma concentrations that are below the lower limit of quantification (LLOQ) will be handled as follows:

- At a time point where less than or equal to 50% of the values are below the LLOQ (BLQ), all BLQ values will be set to LLOQ, and all descriptive statistics will be calculated.
- At a time point where more than half of the values are BLQ, the mean, SD, geometric mean, and CV will be set to Not determined (ND). The maximum value will be reported from the individual data, and the minimum and median will be set to BLQ.
- If all values are BLQ at a time point, no descriptive statistics will be calculated for that time point. Not applicable (NA) will be written in the field for SD and CV and BLQ will be written in fields for mean, geometric mean, minimum, median, and maximum.
- The number of BLO values (n below LLOO) will be reported for each time point.

No imputations will be made for any missing data.

The PK data will be presented by treatment (fed/fasted) in order to estimate the effect of food on the PK of selumetinib.

A healthy volunteer listing and descriptive statistics of all concentration-time data (for selumetinib and N-desmethyl) will be presented by treatment. Data from healthy volunteers excluded from an analysis set will be included in the data listings, but not in the summaries. A listing of PK blood sample collection times as well as derived sampling time deviations will be provided.

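### V_ss/F is calculated as MRT × CL/F from oral data, so it includes absorption time, and its fed and fasted summaries may differ without any change in distribution

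*Protocol*

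**What the plan says.** The synopsis of the protocol lists "apparent volume at distribution equilibrium (V_{ss} /F") among the secondary pharmacokinetic endpoints for selumetinib, together with CL/F, V_z/F and MRT.

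Section 11.2 gives the derivation. The PDF layout has shuffled the line, but the formula is readable: "Apparent volume at distribution equilibrium, mean residence time V_{ss}/F (MRT)*CL/F (selumetinib only"). MRT is named only ("MRT Mean residence time"), with no adjustment for absorption. The method is general: "Pharmacokinetic parameters will be determined using standard noncompartmental methods".

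Both treatments are oral. Sequence 1 in Section 3.1 is "75 mg selumetinib oral dose in a fasted state (Treatment A) followed by a second 75 mg selumetinib oral dose in the fed state", and sequence 2 reverses the order. There is no intravenous reference.

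On what food is expected to do, Section 1.2 says of the earlier food study: "A delay in time to C_{max} (t_{max}) was also observed". It also reports C_max and AUC "being reduced by 62% and 19% respectively under fed conditions".

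On presentation, Section 12.2.4 says: "The PK data will be presented by treatment (fed/fasted) in order to estimate the effect of food on the PK of selumetinib". The same section restricts the mixed model, and the fed/fasted ratios with 90% confidence intervals, to C_max, AUC and AUC_(0-t). It gives t_max a rank-based analysis. V_ss/F therefore receives descriptive statistics by treatment and nothing more.

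**The concern.** The formula in Section 11.2 gives V_ss only when MRT is the residence time of drug already in the circulation. After an oral dose, noncompartmental MRT also counts the time spent being absorbed. The suffix /F accounts for incomplete bioavailability; it does not account for absorption time. The quantity calculated is therefore not the secondary endpoint that the synopsis names.

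In an oral study under one condition this would be a fixed upward offset of modest interest. Here the factor under study is food, which may change absorption time. If it does, the offset differs between the two columns of the table, and a reader could take the difference for a food effect on distribution. What is at stake is the reading of one secondary, descriptive parameter under the objective of characterising selumetinib pharmacokinetics fed and fasted.

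**Working it through.** **Plan's own figure.** The protocol states no value for V_ss/F, MRT, MAT or half-life, so there is nothing to reproduce. The bias follows from algebra; its size rests on assumed inputs.

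**Identity.** For linear kinetics after an oral dose, with MRT_d the disposition residence time:

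- MRT_oral = MRT_d + MAT
- MRT_d × CL/F = V_ss/F
- so MRT_oral × CL/F = V_ss/F + MAT × CL/F
- relative excess = MAT / MRT_d
- fed/fasted ratio, with true volume, CL and F unchanged = (MRT_d + MAT_fed) / (MRT_d + MAT_fasted)

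**Assumed inputs.** Half-life 5 to 10 h; MAT 0.5 to 1 h fasted and 1.5 to 3 h fed. With one compartment MRT_d = half-life / ln 2, which is 7.21 h at 5 h and 14.43 h at 10 h.

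**Excess over true V_ss/F.**

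| | Smallest | Largest |
|---|---|---|
| Fasted | 0.5/14.43 = 3% | 1/7.21 = 14% |
| Fed | 1.5/14.43 = 10% | 3/7.21 = 42% |

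**Spurious fed/fasted ratio (true ratio 1.00).**

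- Smallest: (14.43 + 1.5)/(14.43 + 1) = 15.93/15.43 = 1.03
- Largest: (7.21 + 3)/(7.21 + 0.5) = 10.21/7.71 = 1.32

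**Numerical check at the protocol's sampling times.** A one-compartment oral model was sampled from 0 to 48 h as in Table 3 and analysed with linear-up/log-down AUC and AUMC plus extrapolation. True V was 100 in both states and fasted MAT was 0.5 h. Half-life and fed MAT ranged somewhat wider than above (5 to 12 h, and 2 to 4.3 h).

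| Half-life | Fasted V_ss/F (true 100) | Fed/fasted V_ss/F, fed MAT 2, 3, 4.3 h | Fed/fasted V_z/F |
|---|---|---|---|
| 5 h | 108.3 | 1.19, 1.32, 1.50 | 1.00 to 1.02 |
| 8 h | 105.1 | 1.12, 1.21, 1.33 | 1.00 to 1.01 |
| 12 h | 103.4 | 1.08, 1.14, 1.22 | 1.00 to 1.01 |

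The planned sampling and trapezoidal rule reproduce the algebraic result closely. At a half-life of 5 h, for example, the algebra gives 106.9 for the fasted value.

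**Adding a fall in bioavailability.** Suppose the 19% lower AUC of the earlier study is wholly a fall in F. Every volume divided by F then rises by 1/0.81 = 1.235 with no change in distribution. With fed MAT 3 h, the V_ss/F ratio becomes 1.63, 1.49 and 1.41 at half-lives of 5, 8 and 12 h. The V_z/F ratio is 1.235 in each case. The two effects multiply: 1.235 × 1.318 = 1.63 at 5 h.

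**The case against.** The strongest reply is that nothing the study concludes depends on this parameter. The primary objective is exposure, the sample size rests on AUC and C_max, and V_ss/F has no planned ratio, interval or test. The protocol calls the volume apparent, prints the formula, and reports MRT and t_max beside it, so an informed reader could see a shift in V_ss/F tracking MRT. This stands, and it limits the weight of the point. It does not make the formula right, because nothing in the text says that the value contains absorption time.

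A reader might infer that the plan will declare a food effect on distribution volume. The documents do not support that: they give no interpretation of V_ss/F beyond a summary by treatment. Nor is a larger excess when fed certain. The delay in Section 1.2 was seen in patients given a formulation other than the to-be-marketed capsule, and whether this capsule shows it is part of what the study will measure.

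It is also fair to object that V_z/F is not a clean substitute. A fall in F raises it just as it raises V_ss/F. The numerical check is one-compartment, where V_z and V_ss coincide, so it cannot show that one replaces the other in general. V_z/F would also be distorted if fed absorption became slow enough to govern the terminal slope. All of this stands. The claim for V_z/F is only that its formula carries no MAT term.

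**Conclusion.** The point holds as a wrong formula for a secondary descriptive endpoint. MRT × CL/F from oral data equals V_ss/F + MAT × CL/F, so it overstates V_ss/F in both treatments; that part needs no assumption beyond linear kinetics. An excess that differs between fed and fasted is conditional on food lengthening absorption with this capsule. Under the assumed half-life and MAT ranges, the spurious fed/fasted ratio is about 1.03 to 1.32 with F unchanged. The documents supply none of those inputs, so the range is illustrative and the low end is small.

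The primary endpoints, the modelled ratios and the sample size are untouched. The point is worth correcting because it is cheap to correct, not because it threatens the main result.

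**What to change.** Either of two changes is enough.

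1. Delete V_ss/F from the secondary endpoints in the synopsis and from Section 11.2. V_z/F is already planned and has no MAT term.
2. Keep it, labelled as *MRT × CL/F, includes mean absorption time*, label MRT the same way, and state that a fed/fasted difference in V_ss/F is not to be interpreted as a change in distribution volume.

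Under either option, add that a fed/fasted difference in V_z/F must be read with a possible change in F in mind, given the 19% lower AUC in the earlier study.

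The cost is a line or two in the synopsis and Section 11.2, with one customary descriptive parameter lost or carrying a caveat. Data collection, sample size and the primary analysis do not change.

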12. STATISTICAL METHODS AND SAMPLE SIZE DETERMINATION

12.1 Description of analysis sets

12.1.1 Safety analysis set

All healthy volunteers who received at least one dose of selumetinib will be included in the safety analysis set.

12.1.2 Pharmacokinetic analysis set

All PK analyses will be performed using the PK analysis set. The PK analysis set will consists of all healthy volunteers who receive a dose of selumetinib and provide evaluable PK profiles in at least one study period, without important events or protocol deviations or events thought to significantly affect the PK of the drug (eg, healthy volunteer vomited at or before 2 times median t_{max}; wrong dose administered; prohibited concomitant medication; etc).

A strategy for dealing with data affected by such protocol violations and deviations will be agreed by the Study Pharmacokineticist and the Study Statistician prior to the final analysis.

12.2 Methods of statistical analyses

12.2.1 General principles

Statistical analyses will be performed per Standard Operating Procedures using or higher and, where appropriate, additional validated software.

A healthy volunteer who withdraws prior to the last planned observation in the study period will be included in the analyses up to the time of discontinuation.

Data from non-valid healthy volunteers (healthy volunteers excluded from the analysis set[s]), which are recorded in the database, will only be presented in listings.

The analysis of data will be based on different subsets according to the purpose of analysis, ie, for safety and PK, respectively. The as-treated principle will be applied to all evaluations; ie, healthy volunteers who receive another treatment than the one assigned in the randomization list will be analyzed as belonging to the actual treatment group and not that assigned by randomization.

All derived variables/parameters will be rounded for reporting purposes in the summary tables and healthy volunteer listings, as per Standard Operating Procedures.

12.2.2 Subject characteristics

Continuous variables will be summarized using descriptive statistics (n, mean, standard deviation [SD], minimum, median, maximum) by treatment.

Categorical variables will be summarized in frequency tables (frequency and proportion) by treatment group.

12.2.3 Safety and tolerability

All safety data (scheduled and unscheduled) will be presented in the data listings. Continuous variables will be summarized using descriptive statistics (n, mean, SD, minimum, median, maximum) by treatment. Categorical variables will be summarized in frequency tables (frequency and proportion) by treatment.

Safety variables (eg, clinical laboratory values and vital signs) will be reported to the same precision as the source data. Derived variables will be reported using similar precision to those from which they were derived (eg, QTc derived from QT interval).

Extra measurements (such as unscheduled or repeat assessments) will not be included in the descriptive statistics by scheduled time point, but will be included in data listings. All AEs and clinical laboratory outliers that occur following the first dose of investigational product will be included in the analyses of AEs and outlier events, including episodes that occur at unscheduled evaluations, evaluations, or during the washout period.

All available data from healthy volunteers in the safety analysis set will be included in the safety analyses. No adjustment or imputation will be utilized for missing values or for healthy volunteers who withdraw prior to completing the study, nor will analyses be restricted to healthy volunteers with complete data.

All AEs will be collected for each healthy volunteer from Visit 2 Day -1 until the follow-up visit. All SAEs will be collected for each healthy volunteer from the time when informed consent is obtained until the follow-up visit.

Adverse events will be listed for all healthy volunteers with AEs that occur before dosing indicated on the listing. The number of AEs experienced following administration of the investigational product will be summarized in tables using the MedDRA (Version 13.0 or higher) system organ class and preferred term. These summary tables will also be produced with severity and causality of AEs added as additional classification factors. The number of AEs overall, SAEs, other significant AEs, AEs that lead to withdrawal, AEs of severe intensity, and causally-related AEs will be summarized. Any AE occurring postdose will be considered associated with the last dose of investigational product taken. Adverse events occurring during the washout period and before the second dose of investigational product in Visit 3 will be associated with the last dose. Any AE occurring on Visit 2 Day -1 will not be included in the summaries.

Tabulations and listings of data for vital signs, ECGs, and clinical laboratory tests will be presented, as appropriate. Results from physical examinations will be presented separately in listings only. All continuous safety data will be summarized across all treatments for the absolute value at each scheduled assessment and for the corresponding change-from-baseline. For clinical laboratory tests, listings of values for each healthy volunteer will be presented

with abnormal or out-of-range values flagged. Clinical laboratory data will be reported in Système International units in the clinical study report. Additional graphical presentations of the data eg, shift plots comparing baseline to on treatment values will be generated as appropriate to aid the interpretation of safety data.

12.2.4 Pharmacokinetics

For qualitative variables, the population size (sample size and available data) and the percentage (of available data) for each class of the variable will be presented. Quantitative variables will be summarized using descriptive statistics, including available data, arithmetic mean, SD, coefficient of variation (CV), median, minimum, and maximum values. Additionally, geometric means and geometric CV will be reported for PK variables, except for t_{max} . The geometric mean is calculated as the exponential of the arithmetic mean calculated from data on a log scale. The geometric CV is calculated as $100*[exp(s^2)-1]^{1/2}$; where s is the SD of the data on a log scale. Mean, SD, CV, geometric mean, and geometric CV will not be calculated for t_{max} ; t_{max} will be summarized using median and range.

Plasma concentrations that are below the lower limit of quantification (LLOQ) will be handled as follows:

- At a time point where less than or equal to 50% of the values are below the LLOQ (BLQ), all BLQ values will be set to LLOQ, and all descriptive statistics will be calculated.
- At a time point where more than half of the values are BLQ, the mean, SD, geometric mean, and CV will be set to Not determined (ND). The maximum value will be reported from the individual data, and the minimum and median will be set to BLQ.
- If all values are BLQ at a time point, no descriptive statistics will be calculated for that time point. Not applicable (NA) will be written in the field for SD and CV and BLQ will be written in fields for mean, geometric mean, minimum, median, and maximum.
- The number of BLO values (n below LLOO) will be reported for each time point.

No imputations will be made for any missing data.

The PK data will be presented by treatment (fed/fasted) in order to estimate the effect of food on the PK of selumetinib.

A healthy volunteer listing and descriptive statistics of all concentration-time data (for selumetinib and N-desmethyl) will be presented by treatment. Data from healthy volunteers excluded from an analysis set will be included in the data listings, but not in the summaries. A listing of PK blood sample collection times as well as derived sampling time deviations will be provided.

Figures of geometric mean and \pm geometric SD concentration-time data for each treatment will be presented for plasma selumetinib and N-desmethyl selumetinib concentrations separately, on linear and semi-logarithmic scales. Individual healthy volunteer concentration-time data for each analyte will be graphically presented separately on linear and semi-logarithmic scales. Scatterplots of the individual parameter data (C_{max} , AUC, and AUC_(0-t)) and geometric means will be presented by analyte, treatment, and parameter, with lines connecting the individual parameters and geometric means across the two treatments. Graphical presentations of other PK data may be added at the discretion of the pharmacokineticist.

For statistical evaluation of food effect, log-transformed, C_{max} , AUC, and AUC_(0-t) of selumetinib and N-desmethyl selumetinib will be separately analysed using a linear mixed-effects analysis of variance model with sequence, period, and treatment as fixed effects, and healthy volunteer nested within sequence as a random effect. Transformed back from the logarithmic scale, geometric least-squares means together with confidence intervals (CIs) (2-sided 95%) for C_{max} , AUC, and AUC_(0-t) will be estimated and presented. Also, ratios of geometric least squares means (fed/fasted) together with CI (2-sided 90%) will be estimated and presented.

An analysis of selumetinib and N-desmehtyl selumetinib t_{max} using the Wilcoxon Signed Rank Test, and the Lehman median estimator of difference (fed-fasted) and 90% CIs will also be presented.

Analyses will be conducted separately for selumetinib and the metabolite N-desmethyl selumetinib, however, it should be noted that sample size was determined according to the precision of the food effect of selumetinib, rather than the metabolite.

These analyses of food effect will require healthy volunteers to have evaluable PK data in both study periods.

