12.3 Determination of sample size

The primary objective of this study is to investigate the effect of food, in comparison to fasting conditions, on the exposure of selumetinib after a single 75 mg dose in healthy volunteers.

Data from a previous food effect study (Study D1532C00020) indicated a significant effect of food on the exposure of selumetinib, the geometric least squares means C_{max} and AUC were reduced by 62% and 19% respectively under fed conditions compared to fasted conditions. Consequently, this study has been sized to be able to estimate the fed/fasted effect on exposure with a good degree of precision.

A sample size of 30 evaluable healthy volunteers has been selected based on the desire to gain adequate information while exposing as few healthy volunteers as possible to study

procedures. Thirty-four healthy volunteers (17 per sequence group) will be randomized into the study in order to have at least 30 evaluable healthy volunteers complete the study (allowing for an approximate 10% dropout rate).

Table 8 displays expected 90% and 95% CIs for a range of possible fed/fasted ratios at the selected sample size of 30 evaluable healthy volunteers. Within-subject estimates of CV (16.9% for AUC and 34.0% for C_{max}) observed in a prior clinical study (D1532C00066) were used in these calculations. These CIs demonstrate that good precision of the food effect will be achieved from a sample size of 30 evaluable healthy volunteers.

Table 8 90% and 95% confidence intervals for C_{max} and AUC, varying fed/fasted ratios and using a sample size of 30

		Reduction of C_{max} , food effect, fed versus fasted (geometric least squares means ratio)				
Para- meter	Confidence Interval	62% (0.38)	70% (0.3)	60% (0.4)	50% (0.5)	40% (0.6)
C_{max}	90%	0.33, 0.44	0.26, 0.35	0.35, 0.46	0.43, 0.58	0.52, 0.69
C_{max}	95%	0.32, 0.45	0.25, 0.35	0.34, 0.47	0.42, 0.59	0.51, 0.71
AUC	90%	0.75, 0.87	0.65, 0.75	0.74, 0.86	0.84, 0.97	0.88, 1.02
AUC	95%	0.74, 0.88	0.64, 0.76	0.73, 0.87	0.83, 0.98	0.87, 1.03

AUC: area under the concentration-time curve in the sampled matrix from time zero to infinity; C_{max} : maximum concentration in the sampled matrix

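### The t_max food-effect analysis ignores period, unlike the C_max and AUC model: the interval stays valid but may lose precision, and a period-adjusted version is nearly free (low severity)

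*Protocol*

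**What the plan says.** Protocol Section 3.1 describes an "open-label, randomized, single-center, 2-period crossover study in healthy male volunteers", with one sequence dosed fasted then fed and the other fed then fasted.

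For C_max, AUC and AUC(0-t), Section 12.2.4 specifies a mixed model "with sequence, period, and treatment as fixed effects, and healthy volunteer nested within sequence as a random effect". The next paragraph turns to t_max for selumetinib and its N-desmethyl metabolite. It is to be analysed "using the Wilcoxon Signed Rank Test, and the Lehman median estimator of difference (fed-fasted) and 90% CIs will also be presented". The statistical methods part of the synopsis says the same. Neither place mentions period or sequence for t_max.

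Three other provisions bear on the point:

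- Section 12.3: "Thirty-four healthy volunteers (17 per sequence group) will be randomized into the study", "allowing for an approximate 10% dropout rate", to leave 30 evaluable.
- Section 12.2.4: the food-effect analyses use only volunteers with evaluable data in both periods.
- Synopsis, number of subjects: withdrawals are not replaced unless the evaluable number drops below 30. Section 5.2.1 gives any replacement the same sequence as the volunteer who left.

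The synopsis lists t_max as a secondary endpoint.

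**The concern.** The signed-rank test and the matching median estimator assume that the paired differences form one sample, symmetric about the food effect. In a two-sequence crossover that holds only if the two periods do not differ. With a period effect, the differences centre on one value in one sequence and on another value in the other. The pooled set is then a mixture, and the randomised sequence that could remove the period effect is not used.

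The same section does use sequence and period for C_max and AUC, and gives no reason for treating t_max differently. The protocol names the method itself, so this is not a detail left to an analysis plan.

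At stake is the precision, and to a small degree the accuracy, of the only inferential t_max comparison. Section 1.2 cites a delayed t_max in the earlier food study, and Section 3.2 gives the rate of absorption as a design aim.

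**Working it through.** **No figure to reproduce.** The protocol states no expected precision for t_max; Table 8 covers only C_max and AUC. I read the named estimator as the one-sample Hodges-Lehmann estimator that accompanies the signed-rank test.

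**Inputs from the protocol.** 17 randomised per sequence and 30 evaluable, hence four losses: 34 − 30 = 4. The evaluable split can be 15/15, 16/14 or, at the extreme, 17/13.

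**Assumed inputs.** Within-subject SD of t_max 0.7 h, so the SD of a paired difference is 0.7 × √2 = 0.99 h. Period effect p (period 2 minus period 1) of 0, 0.25, 0.5 or 1.0 h. Normal errors.

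**Step 1: algebra.** Let τ be the fed-minus-fasted effect.

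- Fasted then fed: fed − fasted centres at τ + p.
- Fed then fasted: fed − fasted centres at τ − p.
- Pooled mean: τ + p(n1 − n2)/(n1 + n2), where n1 is the fasted-then-fed group. The excess is 0 at 15/15, 2/30 = 0.067p at 16/14 and 4/30 = 0.133p at 17/13.
- With equal sequences the variance of the pooled differences rises from σ² to σ² + p². With σ² = 2 × 0.7² = 0.98, the SD grows by √(1 + p²/0.98): 1.03 at 0.25 h, 1.12 at 0.5 h, 1.42 at 1.0 h.
- Period 2 minus period 1 centres at τ + p in the first sequence and −τ + p in the second. Their difference is 2τ, so half of it is τ and p cancels whatever the split.

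**Step 2: simulation.** The one-sample Hodges-Lehmann estimate and 90% CI on pooled differences were compared with half the two-sample Hodges-Lehmann shift on period differences, using thousands of simulated trials per setting.

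| p (h) | Pooled width, 15/15 (h) | Adjusted width, 15/15 (h) | Pooled shift, 16/14 (h) | Pooled shift, 17/13 (h) |
|---|---|---|---|---|
| 0 | 0.63 | 0.65 | 0 | 0 |
| 0.25 | 0.65 | 0.65 | 0.02 | 0.03 |
| 0.5 | 0.71 | 0.65 | 0.04 | 0.07 |
| 1.0 | 0.94 | 0.65 | 0.07 | 0.15 |

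The adjusted estimate showed no shift beyond simulation error in any setting. Repeat runs put the pooled width at p = 1.0 h between 0.92 and 0.94 h. The shift at 17/13 is 13-15% of p, close to the 0.133p from the algebra.

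**Step 3: coverage.** Coverage of the planned interval was about 0.90 with no period effect. At 15/15 it rose to 0.94 at p = 0.5 h and 0.98 at 1.0 h; at 17/13 it was 0.92 and 0.95. It did not fall below nominal beyond simulation error.

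**Step 4: discrete times.** Rounding the differences to 0.5 h, the sampling interval up to 4 h in Table 3, gives the same picture. At p = 1.0 h the widths at 15/15 are 0.94 against 0.65 h, and the shift at 17/13 is 0.14 h.

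**Step 5: how likely is 17/13?** If four of 34 are lost at random, the split is 15/15 with probability C(17,2)²/C(34,4) = 18,496/46,376 = 0.40, 16/14 with 2 × 17 × 680/46,376 = 0.50, and 17/13 with 2 × 2,380/46,376 = 0.10.

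**The case against.** The strongest reply is that the plan names a legitimate paired method and contradicts nothing. Most of the supporting points stand:

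- The protocol gives no evidence of a period effect on t_max. Single doses at least 7 days apart, residence from Day -1 to Day 3 and meals at matching times all make a large one less likely. A 1.0 h effect would be about one SD of a paired difference.
- At p = 0.25 h nothing is gained at 15/15, and with no period effect the adjusted interval is slightly wider.
- A shift of 0.07 or 0.15 h is 4 or 9 minutes, well inside the 0.5 h sampling grid.
- The 17/13 split is the extreme case, with a chance of about 10% if four are lost at random. Losses unrelated to sequence favour neither direction, and replacements take the same sequence.
- t_max is secondary and no decision threshold is attached to it.

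A reader might infer that the planned interval is invalid or overconfident. It is not: a period effect makes it conservative. A reader might also infer that the estimate is biased as planned. Bias needs both a period effect and unequal sequences, and the protocol establishes neither.

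What the reply does not remove is the inconsistency. One section guards against period effects for three parameters and, without a reason, does not for the fourth, although the design supplies what is needed at almost no cost.

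**Conclusion.** This is a cheap improvement of low severity. The named t_max method ignores period in a design randomised by sequence, and differs in this from the protocol's own model for C_max and AUC. The planned interval is valid. With equal sequences the only cost is precision: none at a period effect of 0.25 h, then 0.71 against 0.65 h (about 9% wider) at 0.5 h, and 0.94 against 0.65 h (about 45% wider) at 1.0 h. With unequal sequences a small fraction of the period effect also enters the estimate, at most about 13-15% with 30 evaluable.

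The direction follows from the algebra. The sizes rest on an assumed within-subject SD of 0.7 h, normal errors and assumed period effects, none of which the protocol supplies. The primary food-effect results for C_max, AUC and AUC(0-t) are unaffected.

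**What to change.** In Section 12.2.4 and the synopsis, for both analytes, replace the t_max sentence with the following:

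- Compute each volunteer's period 2 minus period 1 difference in t_max.
- Compare these differences between the two sequences with the Wilcoxon rank-sum test.
- Report half the two-sample Hodges-Lehmann shift, with its 90% CI also halved, signed so that it reads as fed minus fasted.

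The signed-rank result may stay as a supportive analysis. The change is one sentence in two places and a standard procedure. Data collection, conduct and sample size do not change. The downside is an interval about 2-3% wider (0.65 against 0.63 h under the assumptions above) if there is no period effect.
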